### 6.5.3. Concomitant Procedures

A concomitant procedure is any therapeutic intervention (eg, surgery/biopsy, physical therapy) or diagnostic assessment (eg, blood gas measurement, bacterial cultures) performed between the time the participant is enrolled (at screening) and last study visit. Concomitant procedures must be recorded in the eCRF

## 6.6. Dose Modification

No more than a single dose of the study treatment will be administered during this study.

The dose of  $1 \times 10^{12}$  and  $2 \times 10^{12}$  vector genomes/kg body weight will be modified for a participant with BMI  $>30 \text{ kg/m}^2$  (See the table in Section 6.1).

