6. Height (cm) is measured at Screening or Day 0 and at End-of-Study visits (Week 52).

Physical Exam is comprehensive (not targeted) and is performed at all clinic visits.

On Day 0 pre-vector infusion, perform physical exam, obtain height (if not available from Screening) and weight; no need to repeat these evaluations post-vector infusion.

Weight (kg) obtained during Screening (the weight obtained from the most recent visit prior to Day 0) will be used to calculate the dose of FIX protein product for FIX incremental recovery and for the dose of PF-06838435.

7. Vital signs include blood pressure (BP), pulse (P), respiratory rate (RR), and oral temperature (°C/°F), and should be taken after the participant has been resting supine or upright for 5 minutes.

8. At Day 0 (for FIX product infusion), obtain vital sign measurements prior to infusion with FIX protein product.

At Day 0 (for PF-06838435 infusion), obtain vital sign measurements at pre-infusion, 30 ± 2 minutes from the start-of-infusion, end-of-infusion ± 2 minutes, 3 hours ± 10 minutes, 6 hours ± 10 minutes and 24 (±1) hours from the start-of-infusion of PF-06838435.

9. The assessment needs to be completed between Screening visit and pre-vector infusion.

10. Definition of target joint is described in Section 8.10.3. Assessments include identification of target joints and performance of hemophilia joint health score (HJHS).

11. Screening serology will be performed as follows:

For all participants: hepatitis B surface antigen (HBsAg), total hepatitis B core antibody (anti-HBc), HBV-DNA;

For all participants: HCV-RNA load assay;

For HIV-positive participants: CD4+ count and HIV-1 viral load.

Screening Fibroscan (locally), FibroTest/Fibrosure (Central Laboratory [CL]), or AST-to-Platelet Ratio Index (Local Laboratory [LL] & CL) is required to rule out underlying liver disease in all participants without a known pre-existing diagnosis of portal hypertension, splenomegaly, or hepatic encephalopathy.

12. Laboratory Safety Panels:

Hematology – white blood cell (WBC) count and differential, red blood cell (RBC) count, hemoglobin, hematocrit, **CCI** and platelet count; ABO blood group at screening only (if not known at Screening)

Clinical Chemistry – sodium (Na), potassium (K), chloride (Cl), phosphate, carbon dioxide (CO2), glucose, blood urea nitrogen [BUN], and serum creatinine

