#### **4.2. Scientific Rationale for Study Design**

This study will investigate up to three PF-06838435 dose levels ( $5 \times 10^{11}$ ,  $1 \times 10^{12}$ , and  $2 \times 10^{12}$  vg/kg). Safety of these dose levels is supported by previous human clinical trials of AAV2 and AAV8 vectors encoding hFIX, as well as the NHP studies with AAV-Spark100-hFIX19-Padua and with SPK-9001, in which dose levels up to  $5 \times 10^{12}$  vg/kg were infused without evidence of adverse effects.

Dose escalation and dose level expansion strategies are employed in the study based on vector-derived FIX activity levels as well as any immune responses against AAV capsid.

The primary study objective is the assessment of safety and tolerability of a single IV infusion of PF-06838435. This study also aims to characterize kinetics of PF-06838435. The vector-derived endogenous (not affected by intercurrent FIX product infusions) FIX:C activity levels will be characterized by post-treatment population mean. The assessment will be done for each dose of PF-06838435.

As no formal hypotheses will be tested in this study, the sample size is based on the need to establish the initial safety and kinetic profile of PF-06838435. Up to 20 evaluable participants will be dosed in the study ([Section 9.3](#)).

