### 6.1. Study Intervention(s) Administered

Refer to investigational product (IP) manual for specifics on the preparation, storage, handling, disposal, and accountability of investigational product.

ARM Name	PF-06838435/Fidanacogene elaparvovec
Intervention Name	PF-06838435/Fidanacogene elaparvovec
Type	Gene Therapy
Dosage Form	Injectable
Strength	1.00 x 10  vg/mL This is the nominal strength. The actual strength for each lot will be provided for dose calculation
Dosage	5x10  vg/kg single administration 1x10  vg/kg single administration 2x10  vg/kg single administration  For participants with body mass index (BMI) exceeding 30 kg/m  , the study dose will be calculated based on an adjusted body weight

	determination that assumes a maximum permissible BMI of 30 kg/m  . For example, a subject who is 6'2" and weighs 370 pounds (BMI 47.5 kg/m  ) would receive a vector dose based on an adjusted body weight of 234 pounds (which is the body weight associated with a BMI of 30 kg/m  for a 6'2" individual).
Route of Administration	Intravenous infusion/injection
IMP and NIMP	IMP (investigational medicinal product)
Sourcing	Provided centrally by the Pfizer
Packaging and Labeling	Study Intervention will be provided in a 2 mL vial Each vial will be labeled as required per country requirement.
Current/Former Names	PF-06838435, SPK-9001, AAV Spark100 hFIX39-Padua, Adeno associated viral vector with human factor IX Padua gene.

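### Protocol 6.1 applies the BMI dose adjustment at all three dose levels, but 6.6 names only the two higher ones, so the weight basis at the 5×10^11 vg/kg starting dose is not stated consistently

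*Protocol*

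**What the plan says.** Four places in the protocol bear on the weight used for the vector dose.

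- **Section 6.1, dosage row.** The levels 5×10^11, 1×10^12 and 2×10^12 are each listed as "vg/kg single administration". In the same row, for participants with BMI above 30 kg/m², "the study dose will be calculated based on an adjusted body weight", a "determination that assumes a maximum permissible BMI of 30 kg/m"². No level is exempted. The example is a man of 6 ft 2 in who "weighs 370 pounds (BMI 47.5 kg/m"²) and who "would receive a vector dose based on an adjusted body weight of 234 pounds".
- **Section 6.6.** The doses of 1×10^12 and 2×10^12 "vector genomes/kg body weight will be modified for a participant with BMI" above 30 kg/m², with a reference to the table in 6.1. The starting dose is not mentioned.
- **Schedule of Activities, footnote 6.** The screening weight from the most recent visit before Day 0 "will be used to calculate the dose of FIX protein product for FIX incremental recovery and for the dose of PF-06838435". No BMI cap is mentioned.
- **Section 8.4.** The study-specific overdose sentence refers to intended doses of 1×10^12 or 2×10^12 vg/kg and omits 5×10^11.

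The starting dose is still part of the current design. Section 4.2 states: "This study will investigate up to three PF-06838435 dose levels", and the list begins with 5×10^11. The synopsis allows up to 20 evaluable participants at that level, and exclusion criterion 5 refers to it.

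**The concern.** A site that reads 6.1 reaches a capped weight at every level. A site that reads 6.6 together with footnote 6 can reach the screening weight at 5×10^11, because the section headed as dose modification does not list that level. The study-specific overdose sentence does not settle which was intended, since it omits the same level.

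Each participant receives one infusion, so a difference in weight basis cannot average out over later doses. Adverse events, laboratory results and FIX:C activity are summarised by dose group (SAP 9.1, 9.2 and 10.2), and steady-state FIX activity drives escalation and expansion (Protocol 4.1.3.1). If different bases were used within the starting level, one nominal dose group would hold participants dosed by different rules.

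**Working it through.** **Inputs.** Height 6 ft 2 in = 74 in, weight 370 lb, stated BMI 47.5, cap 30 and stated adjusted weight 234 lb, all from the example in Protocol 6.1. Starting dose 5×10^11 vg/kg.

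**Step 1: reproduce the protocol's example.**

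- Height: 74 × 0.0254 = 1.8796 m, so height² = 3.5329 m².
- Weight: 370 × 0.45359 = 167.83 kg.
- BMI: 167.83 / 3.5329 = 47.5, as stated.
- Adjusted weight: 30 × 3.5329 = 105.99 kg = 233.7 lb, which rounds to the stated 234 lb.

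**Step 2: total dose for this participant at the starting level.**

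- Adjusted weight (6.1): 105.99 × 5×10^11 = 5.30×10^13 vg.
- Screening weight (6.6 read literally with footnote 6): 167.83 × 5×10^11 = 8.39×10^13 vg.
- Ratio: 8.39 / 5.30 = 1.58.

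The larger total is 8.39×10^13 / 105.99 = 7.9×10^11 vg per kg of adjusted weight. The smaller total is 5.30×10^13 / 167.83 = 3.2×10^11 vg per kg of actual weight. Neither calculation shows which basis is right.

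**Step 3: general form.** The ratio is (BMI × height²) / (30 × height²) = BMI/30, so it does not depend on height or dose level. The documents give no BMI distribution. The first four BMI values below are assumed; the last is the protocol's example.

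| BMI | Ratio BMI/30 | Difference in total vg |
|---|---|---|
| 31 | 1.03 | +3% |
| 32 | 1.07 | +7% |
| 35 | 1.17 | +17% |
| 40 | 1.33 | +33% |
| 47.5 | 1.58 | +58% |

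Differences are the screening-weight total relative to the adjusted-weight total.

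**The case against.** The strongest reply is that 6.6 is incomplete rather than contradictory. It does not say that only two levels are adjusted or that the starting dose is not. It gives no method of its own and sends the reader to the 6.1 table, where the general rule stands under a list that includes 5×10^11. A site following that reference would probably apply 6.1. This stands: a reader might infer that 6.6 exempts the starting dose, but the text omits that dose and does not exclude it.

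The history also points towards 6.1. The amendment log places BMI-based vector dosing in Amendment 4.0 (May 2016). The note to the study schematic says that no escalation occurred before Amendment 7 (June 2019). Over that period the rule could have operated only at the starting level. This is evidence about past practice, but it does not make the current sections agree.

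Sections 6.6 and 8.4 name the same two levels, so both may have been written for doses still to be given under Amendment 7. Part of that design text is redacted, and future use of 5×10^11 may be limited. That cannot be settled from the documents, and the synopsis, 4.2 and 6.1 still list the level.

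A reader might also infer that participants were misdosed or that dose groups are already mixed. Nothing in the documents shows that sites followed different readings. Nor can the larger total be called an overdose or excess, since that presumes which basis is right. On the analysis side, SAP 7.2.1 already summarises BMI and total vector dose, and SAP 9.3 lists weight, so vg per kg can be derived without a new table.

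**Conclusion.** The inconsistency is real and should be corrected. Section 6.1 covers all three levels, 6.6 and 8.4 leave out the starting level, and footnote 6 states a weight basis without the cap. Read literally, the sections give starting-level totals that differ by BMI/30, which is minor just above BMI 30 and large at the protocol's own example.

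The 58% is a high-BMI illustration and not a typical value. The practical effect depends on three things the documents do not give: how many starting-dose participants exceed BMI 30, which reading sites used, and whether 5×10^11 will be given again. The finding is therefore a wording conflict in a dosing rule that bears on what the starting-dose group means. It is not evidence of a dosing error.

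**What to change.** Reconcile Protocol 6.1, 6.6, Schedule of Activities footnote 6 and 8.4 together. Each named dose level, including 5×10^11, should have one stated weight basis and one intended dose. The choice of basis is the sponsor's. Amending only 6.1 and 6.6 would leave footnote 6 and the overdose sentence unreconciled. The cost is a few lines of protocol text.

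Two optional SAP changes would help. The BMI split in 7.2.1 (<30, ≥30) could match the protocol's trigger (>30). The mismatch affects only a BMI of exactly 30, where the ratio is 30/30 = 1 and the dose is unchanged. The exposure listing could also show the weight used for dosing, so that the basis is visible without derivation. This costs one category label and one listing column.

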## **6.7. Intervention after the End of the Study**

No further intervention is planned after the end of the study.

## **7. DISCONTINUATION OF STUDY INTERVENTION AND PARTICIPANT DISCONTINUATION/WITHDRAWAL**

### **7.1. Discontinuation of Study Intervention**

Since no more than the single infusion of PF-06838435 on Day 1 will be administered during the study, this section is not applicable.

See the Schedule of Activities (SoA) for data to be collected at the time of intervention discontinuation and follow-up and for any further evaluations that need to be completed.

### **7.2. Participant Discontinuation/Withdrawal from Study**

- A participant may withdraw from the study at any time at his/her own request, or may be withdrawn at any time at the discretion of the investigator for safety, behavioral, compliance, or administrative reasons. This is expected to be uncommon.
- At the time of discontinuing from the study, if possible, an early discontinuation visit should be conducted. All assessments outlined for Week 52 visit should be completed. See SoA for data to be collected at the time of study discontinuation and follow-up and for any further evaluations that need to be completed.
- The participant will be permanently discontinued both from the study intervention and from the study at that time.
- If the participant withdraws consent for disclosure of future information, the sponsor may retain and continue to use any data collected before such a withdrawal of consent.
- If a participant withdraws from the study, he/she may request destruction of any remaining samples but data already generated from the samples will continue to be available, and may be used to, to protect the integrity of existing analyses. The investigator must document any such requests in the site study records.
- When a participant withdraws from the study because of an SAE, the SAE must be recorded on the CRF and reported on the CT (clinical trial) SAE Report.

If a participant withdraws from the study after enrollment, but before receiving a dose of the investigational product (PF-06838435), then follow-up beyond the screening evaluations is not required. Withdrawn participants without receiving a dose of the investigational product will be replaced.

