In addition to halting enrollment, such an event will be handled as a serious adverse event (SAE) and reported in the time frame according to [Section 8.3.1.1](#) (Reporting of SAEs to Pfizer) of the protocol. The DMC will review data relevant to the event and will receive input from Pfizer and/or Investigator before providing appropriate recommendations. The event and the DMC's recommendation will be discussed with the U.S. Food and Drug Administration (FDA) and other regulatory authorities prior to re-initiation of enrollment.

All participants who were infused with the investigational product will continue to comply with the follow-up schedule according to the protocol.

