#### **4.5. Extension Study (C0371003)**

Participants who complete study assessments at the defined end of study will be encouraged to enroll in C0371003 evaluating the long-term safety, durability, and efficacy of PF-06838435. A 5-year long-term follow-up (LTFU) is planned based on the November 2006 FDA Guidance entitled Gene Therapy Clinical Trials – Observing Participants for Delayed Adverse Events. The Investigator should discuss the extension plan with the participants prior to enrolling them in this study and again at the End-of-Study (Week 52) visit. Any AEs, safety events or unscheduled visits between Week 52 (or End-of-Study) of this study and the first study visit of the extension study will be captured in the source data for the subject and entered into the extension study database after the subject has agreed and completed the informed consent process.

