#### **8.3.1. Time Period and Frequency for Collecting AE and SAE Information**

The time period for actively eliciting and collecting AEs and SAEs ("active collection period") for each participant begins from the time the participant provides informed consent, which is obtained before the participant's participation in the study (ie, before undergoing any study-related procedure and/or receiving investigational product), through and including last study visit.

For participants who are screen failures, the active collection period ends when screen failure status is determined.

Medical occurrences that begin before the start of study intervention but after obtaining informed consent will be recorded on the Medical History/Current Medical Conditions section of the case report form (CRF) not the AE section.

Follow up by the investigator continues throughout and after the active collection period and until the event or its sequelae resolve or stabilize at a level acceptable to the investigator, and Pfizer concurs with that assessment.

Investigators are not obligated to actively seek AE or SAE after conclusion of the study participation. However, if the investigator learns of any SAE, including a death, at any time after a participant has been discharged from the study, and he/she considers the event to be reasonably related to the study intervention or study participation, the investigator must promptly notify the sponsor.

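### Section 7.2 lets an investigator withdraw an already infused participant, which stops no treatment but ends his scheduled safety observation, contrary to the 52-week commitment to all dosed participants

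*Protocol*

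**What the plan says.** Protocol Section 7.2 provides that a participant "may be withdrawn at any time at the discretion of the investigator for safety, behavioral, compliance, or administrative reasons". The consequence follows in the same section: "The participant will be permanently discontinued both from the study intervention and from the study at that time". An exit visit with the Week 52 assessments is requested where feasible. The section separates dosed from undosed men only in its last paragraph, which waives follow-up beyond screening for those who leave before infusion.

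On treatment, Section 6.6 says: "No more than a single dose of the study treatment will be administered during this study". Section 7.1, on stopping the intervention, says: "Since no more than the single infusion of PF-06838435 on Day 1 will be administered during the study, this section is not applicable". (The infusion day is Day 0 elsewhere.)

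On follow-up, the synopsis (Study Design) and SAP Section 3.1 state without exception that all dosed participants have 52 (±2) weeks of safety observation. Section 4.2 says: "The primary study objective is the assessment of safety and tolerability of a single IV infusion of PF-06838435". After a man leaves, Section 8.3.1 says: "Investigators are not obligated to actively seek AE or SAE after conclusion of the study participation". On the long-term study, Section 4.5 says: "Participants who complete study assessments at the defined end of study will be encouraged to enroll in C0371003".

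In the SAP, Section 9.1 ends the treatment-emergent window at the last visit or at withdrawal. Sections 9.1.2 to 9.1.4 and 9.1.6 base percentages on all subjects of the dose group in the safety analysis set. Section 4 rules out imputation of missing data. Section 5.1 reports discontinuations by primary reason and derives duration on study.

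**The concern.** The withdrawal wording suits a trial with repeated dosing, where withdrawing a participant for safety also ends his exposure. Here the exposure is complete and irreversible after Day 0. For an infused man, discontinuation changes only how closely he is watched.

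Safety is the primary objective, and several primary endpoints (laboratory values, inhibitor development, immune response to capsid) are found by scheduled sampling rather than by complaint. Appendix 6 describes the capsid T-cell reaction as an asymptomatic rise in liver tests and/or a fall in FIX activity. If it first appeared after withdrawal, nobody would be scheduled to look for it. Because safety is one of the listed reasons, the men whose later data are lost may be those at higher risk. Observed incidence would then be too low for a reason linked to the endpoint.

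**Working it through.** The plan states no withdrawal rate and no figure on this point, so there is nothing to reproduce. The check sets the texts side by side and then sizes the loss under stated assumptions.

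**What stops and what remains for an infused man who is withdrawn**

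- Treatment: nothing to stop (Sections 6.6 and 7.1).
- Stops: scheduled laboratory, FIX inhibitor and FIX:C sampling (7.2), and active elicitation of new adverse events (8.3.1).
- Remains: the exit visit where feasible (7.2), follow-up of known events until resolved or stable (8.3.1, 8.3.3), repeat testing of clinically significant abnormal laboratory values (8.2.5), and reporting of later serious events that the investigator learns of (8.3.1.1).
- Commitment not met: observation of all dosed participants for 52 (±2) weeks (synopsis; SAP 3.1).
- Extension: the documents describe a route only for completers (synopsis; 4.5; SAP 3.1) and do not say whether a withdrawn dosed man may enter.

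**Loss for one man**, withdrawn at week w of 52: (52 − w)/52.

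- Week 8: 44/52 = 85%.
- Week 12: 40/52 = 77%.

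**Loss for the cohort.** Let n be the number dosed and k the number withdrawn. Let p_w be the risk of a later new event in a withdrawn man and p_o the risk in each other man. The share of expected later events that goes unseen is k·p_w / [k·p_w + (n − k)·p_o]. The documents give n as about 15 (SAP 3.1), about 20 (Protocol 9.2) or up to 30 (synopsis; SAP 4.1). They give neither k nor the risks.

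At equal risk the share is k/n. For k = 1:

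- n = 15: 1/15 = 6.7%.
- n = 20: 1/20 = 5.0%.
- n = 30: 1/30 = 3.3%.

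At unequal risk, for illustration only, assume p_w = 0.30 and p_o = 0.05 with k = 1:

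- n = 15: 0.30/(0.30 + 14 × 0.05) = 0.30/1.00 = 30%.
- n = 20: 0.30/(0.30 + 19 × 0.05) = 0.30/1.25 = 24%.
- n = 30: 0.30/(0.30 + 29 × 0.05) = 0.30/1.75 = 17%.

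Still with p_o = 0.05 and k = 1, the share runs from 0.15/(0.15 + 0.95) = 14% (p_w = 0.15, n = 20) to 0.50/(0.50 + 0.70) = 42% (p_w = 0.50, n = 15).

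**Precision.** With no events among m men, the one-sided 95% upper limit is 1 − 0.05^(1/m). One loss moves it from 18.1% to 19.3% (15 dosed), from 13.9% to 14.6% (20 dosed) or from 9.5% to 9.8% (30 dosed). Lost precision is minor; the concern is possible bias and missing late data.

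**The case against.** The best case against the point is that withdrawal is expected to be uncommon (Section 7.2) and that the event prompting it would be recorded and followed. SAP 9.1.1 counts a subject once at each level, so a man withdrawn for a drug-related event is already in the overall drug-related count. Only later events under other terms would be missed. SAP 5.1 makes the truncation visible. All of this stands and limits the size. It does not restore scheduled sampling for new, silent findings, and it does not square Section 7.2 with the synopsis.

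Four stronger readings are tempting, but the documents do not support them:

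- A reader might infer that withdrawal bars a man from C0371003. The protocol says only that completers are encouraged to enroll, and the entry criteria of that study are not in the documents.
- A reader might see a direct contradiction with Section 4.3.1: "All participants who were infused with the investigational product will continue to comply with the follow-up schedule according to the protocol". That sentence closes the text on halting enrollment and refers back to the protocol schedule. The conflict lies with the synopsis and SAP 3.1.
- A reader might infer that exit data will be reported as Week 52, because the Schedule of Activities has one column for Week 52 or End-of-Study. No text maps them so, and the rule against imputation does not address visit assignment. The plan is merely silent.
- A reader might want to forbid all investigator-initiated withdrawal. That goes further than needed, and site or study closure (Section 10.1.9) can end follow-up in any case.

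**Conclusion.** The point holds in this form. Section 7.2 permits an investigator to end scheduled safety observation of a man whose exposure is already complete, against the plan's own commitment to observe every dosed participant for 52 (±2) weeks. Because the treatment-emergent window closes at withdrawal while the denominator does not change, later new events go uncounted. Withdrawal for safety can make that loss informative.

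The size cannot be fixed from the documents. For the man concerned it is 85% or 77% of the planned year at Week 8 or 12. For the cohort it is about 5-7% of expected later events per withdrawal, assuming equal risk and 15 to 20 dosed. The larger shares under unequal risk show direction only, since those risks are assumed. Any loss of extension follow-up is an open question, because the plan does not say whether a withdrawn man may enter.

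**What to change.** 1. **Protocol 7.2.** Reconcile it with the synopsis. State that, for infused participants, investigator-initiated discontinuation for the listed reasons does not end safety follow-up. A man who still consents stays on the scheduled safety assessments. If he declines visits, adverse-event contact continues by telephone, a method the synopsis already provides for after Week 52. Withdrawal of consent and site or study closure remain exceptions.
2. **Protocol 4.5.** State whether dosed participants who do not complete Week 52 may be offered C0371003.
3. **SAP.** In Section 9.1.1, add events per participant-year by dose group, using the duration on study already derived in Section 5.1. State that early-discontinuation assessments are tabulated at the week they were taken, not as Week 52.

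The cost is amendment wording in two protocol sections and two SAP sentences. No dose or treatment rule changes. The downside is that sites keep contact with a few poorly compliant participants for longer.
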